9.2 SAMPLE SIZE DETERMINATION

We plan a sample size of 16 patients per treatment arm. Since this is a pilot study, this sample size is largely limited by budgetary restraint and is too small for a sequential study design. However, this sample size is adequate for studying the primary hypothesis with a two-sample two-sided t-test on the mean PGE₂ level at day 28 between the randomized groups. We expect to show that the treatment group has significantly lower mean PGE₂ than the placebo group. In our previous publication on PJ PGE₂,²⁰ we reported that median PJ PGE₂ level in 10 CP patients was 307 pg/ml with IQR of 249-362 pg/ml and standard deviation of 84 pg/ml. The boxplot of that data suggests that normality is a reasonable distributional assumption for the PGE₂ data. That study also found that mean PJ PGE₂ in a healthy control group was 104 pg/ml, about one third of the mean level of the CP group. If we conservatively assume that the control group in the proposed trial has 50% decrease in mean, with a Type I error of 0.05, the power of the t-test is 0.998. If we use an even more conservative mean for the control group, with 1/3 reduction in mean PGE₂, the power is 0.94. If we additionally assume that there is some data loss (due to consent withdrawal, dropout, or specimen mishandling) so that the sample size per treatment group is 12 instead of 16, the statistical power decreases to 0.85, but is still reasonable. Note that the large statistical power in the calculation above is a result of the relatively small standard deviation of the PGE₂ compared with our working assumption on the mean reduction. This assumption is supported by the data in Abu Dayyeh et al.²⁰ If this pilot study is successful, we will conduct a future study that focuses on patient centered outcomes; that study is expected to have a larger sample size because those outcomes are expected to be less sensitive to the treatment than biomarkers. The data from this pilot study will provide critical preliminary and feasibility data for the future investigation.

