4 STUDY DESIGN

4.1 OVERALL DESIGN

This is a phase 1 / 2, randomized, placebo-controlled, double-blinded study of oral indomethacin 50 mg po BID vs. placebo po BID in patients with chronic pancreatitis. The study will be conducted at Mayo Clinic Rochester and Ohio State University.

The study **hypothesis** is:

- 1) That mean pancreatic juice PGE₂ concentration will decrease after indomethacin treatment to no more than 66% of baseline, and will be significantly lower than after placebo treatment.

[figure not shown]
Exploratory hypotheses are:

- 1) That peak blood IN levels at the conclusion of treatment will correlate with degree of change in pancreas juice (PJ) PGE₂ concentrations.
- 2) That baseline salivary and blood PGE₂ concentrations, and changes in these concentrations after treatment, will correlate with blood and saliva PJ PGE₂ concentrations.
- 3) That improvement in pain and quality of life of study participants will correlate with changes in PJ PGE₂ concentrations.

Overview: 32 participants with CP will be randomized to receive 28 days of IN 50 mg po BID or placebo (2 study arms). Blood, saliva, and pancreatic juice will be collected from each participant prior to study drug administration and again on the 28th day of study drug administration. Participants will complete daily pain diaries as well as questionnaires assessing pain and quality of life at baseline and day 28. Primary outcome is a comparison of the mean change in PJ PGE₂ concentrations at 28 days in the IN vs. placebo groups. Secondary outcomes include changes in

pain and quality of life from baseline to 28 days in the IN vs. placebo groups, and their correlation with changes in PJ PGE₂ and blood IN concentrations, as well as correlation of PJ, saliva, and blood PGE₂ concentrations (to determine whether non-invasive measures correlate with PJ measures).

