We propose a sample size of 16 patients per treatment arm. Since this is a pilot study, this sample size is largely limited by budgetary restraint. However, this sample size is adequate for studying the primary hypothesis with a two-sample two-sided t-test on the mean PGE₂ level at day 28 between the randomized groups. We expect to show that the treatment group has significantly lower mean PGE₂ than the placebo group. In our previous publication on PJ PGE₂,²⁰ we reported that median PJ PGE₂ level in 10 CP patients was 307 pg/ml with IQR of 249-362 pg/ml and standard deviation of 84 pg/ml. The boxplot of that data suggests that normality is a reasonable distributional assumption for the PGE₂ data. That study also found that mean PJ PGE₂ in a healthy control group was 104 pg/ml, about one third of the mean level of the CP group. If we conservatively assume that the control group in the proposed trial has 50% decrease in mean, with a Type I error of 0.05, the power of the t-test is 0.998. If we use an even more conservative mean for the control group, with 1/3 reduction in mean PGE₂, the power is 0.94. If we additionally assume that there is some data loss (due to consent withdrawal, dropout, or specimen mishandling) so that the sample size per treatment group is 12 instead of 16, the statistical power decreases to 0.85, but is still reasonable. Note that the large statistical power in the calculation above is a result of the relatively small standard deviation of the PGE₂ compared with our working assumption on the mean reduction. This assumption is supported by the data in Abu Dayyeh et al.²⁰ If this pilot study is successful, demonstrating a statistically significant indomethacin-related decrease in PJ PGE₂ by at least 1/3, we will conduct a future study that focuses on patient centered outcomes; that study is expected to have a larger sample size because those outcomes are expected to be less sensitive to the treatment than biomarkers. Only if indomethacin treatment achieves this result would longer-term trials of indomethacin at this dose be warranted. The data from this pilot study will provide critical preliminary and feasibility data for the future investigation.

Timeline and Feasibility: Both Mayo Clinic Rochester (MCR) and Ohio State University (OSU) medical centers feature busy medical pancreatology practices. Average monthly new patient

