4.2 SCIENTIFIC RATIONALE FOR STUDY DESIGN

The study rationale is presented in the Introduction section of this protocol. A placebo control group was chosen to adequately control for changes in PJ PGE₂ that might occur over time due to other clinical and disease factors. A physiologic primary endpoint is being studied and the study is powered to identify superiority of IN over placebo.

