9 STATISTICAL CONSIDERATIONS

9.1 STATISTICAL HYPOTHESES

Primary Endpoint:

- Decrease in mean pancreatic juice PGE₂ concentration after indomethacin treatment, to no more than 66% of baseline, and statistically significant in comparison to placebo.

Secondary Efficacy Endpoints:

- Changes in salivary and blood PGE₂ concentrations after study drug administration will have statistically significant correlation with changes in PJ PGE₂ concentrations and blood IN levels.
- Salivary and blood PGE₂ concentrations will have statistically significant correlation with PJ PGE₂ concentrations.
- Improvement in pain and quality of life of study participants will have statistically significant correlation with post-treatment changes in PJ PGE₂ concentrations.
- Exploratory analysis of molecular analytes (cytokine and microbiome) in blood and saliva will be done to measure effect of IN administration.

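### The stated power of 0.998, 0.94 and 0.85 covers only the day-28 comparison with placebo; at the 1/3 reduction behind 0.94 and 0.85, the two-part primary endpoint is met about half the time at most

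*Combined protocol and SAP*

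**What the plan says.** The primary endpoint has two parts. Section 9.1 asks for a fall in mean pancreatic juice PGE₂ after indomethacin "to no more than 66% of baseline, and statistically significant in comparison to placebo"; the synopsis (1.1) and section 3 say the same. The study hypothesis in section 4.1 repeats both parts: the mean "will decrease after indomethacin treatment to no more than 66% of baseline, and will be significantly lower than after placebo treatment". The statistical part of section 4.1 then defines success as "demonstrating a statistically significant indomethacin-related decrease in PJ PGE₂ by at least 1/3" and makes that result the condition for longer-term trials at this dose.

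The sample size text, given in both 4.1 and 9.2, says "this sample size is adequate for studying the primary hypothesis with a two-sample two-sided t-test on the mean PGE₂ level at day 28". Three figures follow:
- a 50% reduction with 16 per arm: "with a Type I error of 0.05, the power of the t-test is 0.998"
- a 1/3 reduction with 16 per arm: "with 1/3 reduction in mean PGE₂, the power is 0.94"
- a 1/3 reduction with 12 per arm: "the statistical power decreases to 0.85, but is still reasonable"

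Section 4.2 adds that "the study is powered to identify superiority of IN over placebo". Nowhere do the documents give the probability of meeting the 66% part, alone or together with the placebo comparison. They do not say whether that part is judged on observed means or in some other way. They also leave its scale open, because section 9.4.2 allows a transformation.

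**The concern.** The primary hypothesis has two conditions, and the sample size is called adequate for it on power for one of them. The omitted condition is the one that matters at 1/3: that reduction leaves 66.7% of baseline, just above a 66% cut and exactly on a 2/3 cut.

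The decision on longer-term trials rests on the joint result. A reader who takes 0.94, or 0.85 after data loss, as the chance of a positive trial at a true 1/3 reduction would expect a go decision nearly every time. If the rule for the 66% part is left open, it can also be settled after the data are seen.

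**Working it through.** **Inputs.** From 9.2: CP median 307 pg/ml (used here as the mean), SD 84, normality, two-sided alpha 0.05, 16 or 12 per arm, reductions of 50% and 1/3. The text attaches the reduction to the control group; I read this as the indomethacin arm, as the neighbouring sentences require. Assumed, because the documents do not give them: SD 84 at both visits in both arms, placebo mean unchanged, untransformed data, correlation ρ between baseline and day 28 from 0 to 0.8, and the cut applied to observed means in the indomethacin arm.

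**Step 1: the plan's own figures.** Normal approximation: power = Φ(δ / (84·√(2/n)) − 1.96).
- 50%, n = 16: δ = 153.5, SE = 29.70, ratio 5.17, power 0.999 (stated 0.998).
- 1/3, n = 16: δ = 102.3, ratio 3.45, power 0.931 (stated 0.94).
- 1/3, n = 12: SE = 34.29, ratio 2.98, power 0.847 (stated 0.85).

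The exact t-test gives 0.999, 0.915 and 0.814. Either way, the stated figures are clearly those of the placebo comparison alone.

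**Step 2: the cut alone.** With true reduction r and cut c, day-28 mean minus c × baseline mean in the indomethacin arm is normal with mean 307·(1 − r − c) and SE 84·√((1 + c² − 2cρ)/n). So P(cut met) = Φ(307·(c − (1 − r)) / SE).
- r = 1/3, c = 0.66, n = 16: the numerator is 307 × (0.66 − 0.6667) = −2.05. At ρ = 0, SE = 21 × √1.4356 = 25.16 and P = Φ(−0.081) = 0.468. At ρ = 0.8, SE = 21 × √0.3796 = 12.94 and P = Φ(−0.158) = 0.437.
- r = 1/3, c = 2/3: the numerator is zero, so P = 0.50 for any n and ρ.
- r = 40%, c = 0.66, n = 16: the numerator is 18.42; P = 0.768 (ρ = 0) to 0.923 (ρ = 0.8).
- r = 50%, c = 0.66, n = 16: the numerator is 49.12; P = 0.975 to 1.000.

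Joint power cannot exceed these values.

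**Step 3: both parts together.** Simulation of bivariate normal baseline and day-28 pairs, at least 60,000 trials per cell, ρ = 0, 0.3, 0.5, 0.7 and 0.8. Success means the observed ratio is at or below the cut and two-sided p < 0.05 favours indomethacin. Two tests were run: the day-28 t-test named in 9.2, and the comparison of change. In balanced complete data the latter equals the group-by-time contrast of the random intercept model in 9.4.2.

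| True reduction | n per arm | Cut | Day-28 t-test | Change contrast |
|---|---|---|---|---|
| 1/3 | 16 | 66% | 0.43-0.46 | 0.41-0.45 |
| 1/3 | 16 | 2/3 | 0.49 | 0.43-0.50 |
| 1/3 | 12 | 66% | 0.42-0.44 | 0.36-0.45 |
| 1/3 | 12 | 2/3 | 0.46-0.47 | 0.37-0.50 |
| 40% | 16 | 66% | 0.76-0.91 | 0.69-0.92 |
| 50% | 16 | 66% | 0.97-0.999 | 0.93-1.00 |

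**The case against.** The strongest reply is that the plan does not hide what it computed. Sections 4.1 and 9.2 name the t-test and the day-28 comparison, section 4.2 says the study is powered for superiority over placebo, and one sentence in 4.1 words the primary outcome as a between-arm comparison of mean change. This stands in part: the figures are labelled. But the same text calls the sample size adequate for the primary hypothesis, which has two parts, and no joint figure follows.

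Second, any rule based on an observed mean passes about half the time when the truth lies on the cut. That is true, and it is ordinary behaviour for a minimum-effect threshold. The point is only that 0.94 and 0.85 are quoted at exactly that place. The plan treats 1/3 as more cautious than its already cautious 50%, and at 50% joint power is high.

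Third, this is a pilot limited by budget, and section 4.1 admits the small sample may prevent significance. Accepted; no further participants are asked for.

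Three stronger readings are tempting, and the documents do not support them:
- *The go rule is met clearly less than half the time at a true 1/3 reduction.* That follows from a 66% cut. Section 4.1 words the go rule as at least 1/3, for which the range is 0.43-0.50.
- *The 66% part needs its own significance test, with far lower power.* No section specifies such a test.
- *The t-test figures are miscalculated or the sample is too small.* The figures reproduce closely by normal approximation, and the ceiling at 1/3 comes from where the cut lies: in step 2, the 2/3 cut gives 0.50 for any n.

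**Conclusion.** The concern holds as a gap in what the stated power covers. At a true 1/3 reduction, the two-part endpoint is met about 0.41-0.46 of the time with 16 per arm and a 66% cut, or 0.43-0.50 with a 2/3 cut, against a stated 0.94. With 12 per arm the ranges are 0.36-0.45 and 0.37-0.50, against 0.85. The shortfall belongs to those two scenarios. At 50% with 16 per arm and a 66% cut, joint power is 0.93-1.00 (0.97-0.999 on the day-28 t-test), close to the stated 0.998.

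The omission itself is certain from the text. The sizes rest on the assumptions listed in the working: mean 307, SD 84 at both visits, an unchanged placebo mean, correlation 0 to 0.8, untransformed data, and a cut judged on observed means. The documents do not confirm the last of these, so the ranges describe one reasonable reading of the rule.

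**What to change.** In sections 9.2 and 4.1:

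1. State that 0.998, 0.94 and 0.85 are power for the placebo comparison only, and not for the two-part primary endpoint.
2. Add a small table of joint power at true reductions of 1/3, 40% and 50%, with its assumptions (mean, SD, correlation range, scale, test). Note that at 1/3 both parts are met about half the time at most if the cut is judged on observed means.
3. Use one threshold, 66% or 1/3, throughout the synopsis and sections 3, 4.1 and 9.1. State that it is judged on observed means, or how otherwise, and on which scale, given the transformation allowed in 9.4.2.

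The cost is a few sentences and one table. The stated power will look less favourable, and the sponsor must commit to a rule for the 66% part before the data are seen. Sample size and conduct stay as they are.

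### The three stated power values (0.998, 0.94, 0.85) cannot all be obtained from the stated t-test and SD; for a one-third reduction the printed values are about 2 to 4 points too high on the figures given

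*Combined protocol and SAP*

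**What the plan says.** Section 9.2 sets the size ("We plan a sample size of 16 patients per treatment arm") and names the test: "this sample size is adequate for studying the primary hypothesis with a two-sample two-sided t-test on the mean PGE₂ level at day 28". The reference data come from an earlier study by the same group: "median PJ PGE₂ level in 10 CP patients was 307 pg/ml with IQR of 249-362 pg/ml and standard deviation of 84 pg/ml". The mean of the chronic pancreatitis (CP) patients is not given. The text says only that the healthy-control mean, 104 pg/ml, is roughly one third of it.

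Three power values follow:

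- For a 50% reduction with 16 per arm: "with a Type I error of 0.05, the power of the t-test is 0.998".
- For a one-third reduction with 16 per arm: 0.94.
- For a one-third reduction after data loss: "so that the sample size per treatment group is 12 instead of 16, the statistical power decreases to 0.85, but is still reasonable".

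The reduction is attached to the wrong arm: "If we conservatively assume that the control group in the proposed trial has 50% decrease in mean". The one-third scenario does the same. Section 4.1 carries the same calculation ("the statistical power decreases to 0.85, but is still reasonable"). Neither section says whether the power came from the noncentral t distribution or from a normal approximation.

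**The concern.** A stated power should be recoverable from the test, alpha, SD, difference and sample size printed beside it. Here a direct calculation with the printed centre and SD gives lower values for both one-third scenarios. The one-third reduction is the scenario that matters most, because Section 4.1 makes a significant fall of at least that size the condition for longer trials at this dose. If the lower values are right, the chance of missing a true one-third reduction is 8.5% rather than 6% with 16 per arm, and 18.6% rather than 15% with 12. The wording about the control group also makes the assumption, read literally, a fall on placebo.

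**Working it through.** **Inputs** (Section 9.2): two-sided two-sample t-test; alpha 0.05; SD 84 pg/ml in both arms; normal data on the untransformed scale; n = 16 or 12 per arm; reduction of 1/2 or 1/3. The CP mean is not stated. Two values can be taken from the text: 307 (the reported median, used as a mean under the plan's normality assumption) and 3 × 104 = 312.

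**Formula.** For a difference δ, the noncentrality parameter is ncp = (δ/SD) × √(n/2), with df = 2n − 2. Power is the probability that a noncentral t with these parameters falls beyond ±t(0.975, df). The critical values are 2.042 at df 30 and 2.074 at df 22.

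**At 307.**

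- One third: δ = 307/3 = 102.3 and δ/SD = 1.218.
  - n = 16: ncp = 1.218 × √8 = 3.446, power 0.915 (plan: 0.94).
  - n = 12: ncp = 1.218 × √6 = 2.984, power 0.814 (plan: 0.85).
- One half: δ = 153.5, n = 16: ncp = (153.5/84) × √8 = 5.169, power 0.9988 (plan: 0.998).

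**Attempts to recover the plan's values, all with SD 84.**

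| Method and CP mean | 50%, n=16 | 1/3, n=16 | 1/3, n=12 |
|---|---|---|---|
| Plan as printed | 0.998 | 0.94 | 0.85 |
| t-test, 307 | 0.9988 | 0.915 | 0.814 |
| t-test, 312 | 0.9991 | 0.923 | 0.826 |
| t-test, 323 | 0.9995 | 0.939 | 0.851 |
| Normal approximation, 307 | 0.9993 | 0.931 | 0.847 |
| Normal approximation, 312 | 0.9995 | 0.939 | 0.858 |

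**Can one mean give all three?** Each printed value was inverted, allowing for rounding.

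- *t-test.* A value of 0.998 needs a mean of about 293 to 303. Values of 0.94 and 0.85 together need about 320 to 325. The ranges do not overlap.
- *Normal approximation.* A value of 0.998 needs about 283 to 293. The other two together need about 309.5 to 310.5. Again there is no overlap.
- *Truncation.* Reading 0.998 as cut off rather than rounded extends the first range only to about 310 under the t-test and 300 under the normal approximation. Neither gap closes.

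Power depends on the mean only through its ratio to the SD, so changing the common SD does not help. An SD of about 80 with 307 returns 0.94 and 0.85 under the t-test, but the 50% case then overshoots in the same way.

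**Sensitivity to the SD** (t-test, 307, one-third reduction, 16 per arm): power is 0.80 at SD 100 and 0.65 at SD 120.

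**The case against.** The strongest reply is that the inputs are incomplete, not wrong. The 307 is a median, the reductions are in the mean, and the true CP mean lies in a cited paper. A mean of about 323 is compatible with the text (104/323 = 0.32, still about one third) and returns 0.94 and 0.85 under the named test. The normal approximation at 307 also comes within a point of both. This stands to the extent that a reader might infer 0.915 and 0.814 to be simply the correct values; the documents do not support that without knowing the mean. It does not rescue the printed set. The normal approximation is not the named test and runs high at 30 and 22 degrees of freedom, and a mean near 323 contradicts the printed 0.998.

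Three further points on the plan's side stand:

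- The text already attributes the SD to 10 CP patients and says that the high power rests on its small size. A reader might infer that this dependence is concealed; it is not. Only a range of SDs is missing.
- The control-group wording is a slip. The same paragraph expects the treated arm to be lower than placebo, and two-sided power is unaffected by which arm falls.
- The sample size is set mainly by budget, Section 4.1 concedes that it may be too small for significance, and the primary analysis is a random intercept model that also uses baseline data. The t-test power is therefore a planning approximation.

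**Conclusion.** The stated power is not sound as written. On either centre that the documents supply, the t-test values for a one-third reduction are 0.915 to 0.923 with 16 per arm and 0.814 to 0.826 with 12. The printed values are therefore about 2 to 4 points too high. No single mean with SD 84 gives all three printed values under the t-test or the normal approximation. The 0.998 is, if anything, slightly low, which is of no consequence.

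This rests on equal SDs of 84 in both arms, normal data and two-sided alpha 0.05, all as the plan assumes. A reader might infer that the trial is underpowered or needs more patients. The figures do not show that: at SD 84 power stays at about 0.81 or more in every one-third scenario. The impact is minor, and the point is one of accuracy and traceability.

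**What to change.** In Sections 9.2 and 4.1:

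1. State the CP mean actually used, and that power is computed from the noncentral t distribution.
2. Recompute all three values. If 307 and SD 84 stand, print 0.999, 0.915 and 0.81.
3. In both reduction scenarios, name the indomethacin group instead of the control group.
4. Optionally, add one line giving power at SD 100 and 120 (0.80 and 0.65 with 16 per arm, one-third reduction from 307).

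The cost is a wording change in two sections and a slightly less favourable power statement. Enrolment, procedures and analysis are unchanged.

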9.3 POPULATIONS FOR ANALYSES

Given the small sample size of this pilot study, the entire study population completing the study protocol will be utilized for most analyses. Per-Protocol analysis will be used primarily (e.g., participants who took at least 80% of study intervention for 80% of the days within the treatment period).

